The study described within this protocol is designed to test the efficacy of a new insulin-only closed-loop algorithm using a model predictive control (MPC) framework that will incorporate a new feature to handle meals that are consumed without a pre-bolus of insulin called the Robust AP (R-AP) system. Model predictive control (MPC) is a control strategy whereby a model is used to predict the response of a system to a receding horizon of inputs. MPC uses the model to predict how the system will respond to current and future inputs and selects an optimal control output based on how well the predicted output of the system matches an optimal control trajectory. The power of MPC is in its predictive ability such that systems, which have very long response times, can be modelled to avoid over or under-delivery of control outputs of the MPC algorithm to the system which thereby lead to instability. An early paper describing an approach to MPC using a glucoregulatory model was Hovorka et al. [16]. This group has gone on to use MPC within their single-hormone control system, which has been evaluated clinically [14]. The group at University of Virginia developed an MPC for use within an AP [17] and they have published results on this algorithm within a multi-center trial [18]. The Padova group has also done work on MPC algorithms within an AP including an algorithm that uses an auto-regressive model that adapts over time called a run-to-run algorithm [19].

The robust R-AP system used in this protocol has been designed to handle a variety of real-world scenarios that are critical to a high-risk patient population. We will test how well the new algorithm handles missed or inaccurate meal announcements. This type of algorithm may significantly improve glucose control over the standard model predictive control (MPC) closed-loop algorithm without these new algorithm features for patients with type 1 diabetes.

Primary Objectives:

• To evaluate performance of the OHSU Robust R-AP closed-loop system as measured by area under the curve (AUC) in the 4 hours following first meal period, versus the OHSU MPC closed-loop system.

• To evaluate performance of the OHSU Robust R-AP closed-loop system as measured by percent of time with sensed glucose between 70 – 180 mg/dl in the 4 hours following the first meal period, versus the OHSU MPC closed-loop system.

Secondary Objective:

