• To evaluate performance of the OHSU Robust R-AP closed-loop system versus the OHSU MPC closed-loop system in the 4 hours following the first meal period, as measured by other glycemic outcomes.

Study Hypothesis:

We propose that the use of the OHSU Robust R-AP closed-loop system as compared to the OHSU MPC closed-loop system will decrease AUC and increase the time in range as measured by sensed glucose values.

Endpoints

Primary Endpoint:

- Incremental AUC of postprandial glucose in the 4 hours following the start of first meal. AUC (mg/dL*min) will be calculated using a trapezoidal method [20], which sums all CGM values in the 4 hour period following the meal above the starting glucose.
- Percent of time with sensed glucose between 70 180 mg/dl in the 4 hours following the start of first meal.

Secondary Endpoints (all measured in the 4 hours following the start of meals):

- Percent of time with sensed glucose <70 mg/dl across the study duration
- Number of carbohydrate treatments (defined as 15 or 20 grams of carbohydrate)
- Number of provider-administered insulin injections due to hyperglycemia
- Mean sensed glucose
- Percent of time with sensed glucose <54 mg/dl
- Percent of time with sensed glucose >180 mg/dl
- Percent of time with sensed glucose >250 mg/dl
- Mean amount of insulin delivered per day (in units/kg)

Study Type

This is a single-center, crossover trial designed to compare the glucose control resulting from the use of the OHSU Robust R-AP system as compared to the OHSU MPC AP system.

Study Population

Study population will be adults with type 1 diabetes, ages 18-65 years of age. Younger participants are excluded as it is appropriate to assess safety first in the adult population. Fifteen participants will be recruited to participate in studies.

[figure not shown]
Power Analysis

This study is to obtain feasibility and assessment of variability in the primary outcomes that will inform a future larger, sufficiently powered efficacy study. A sample size of 15 is a feasible number to recruit and complete the study in timely fashion. This sample size will allow adequate estimation of the outcomes and variability of those estimates.

Protocol Summary:

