The R-AP is a modified MPC algorithm. A new feature in the algorithm includes a model for missed meal insulin detection. The model includes estimations for carbohydrate consumption based glucose patterns to determine if that person has consumed a meal without announcing it to the system. We refer to this algorithm as Missed Meal Insulin Detection. Our Missed Meal Insulin Detection algorithm is unique in that it presumes that the patient will generally announce their meals to the system. However, if the participant does not announce, the algorithm will detect it using machine learning methods, and then adjust dosing based on this detected meal.

Statistical methods

The primary study endpoints are (1) incremental area under the curve (AUC) of glucose in the 4 hours following unannounced meals and (2) percent of time with glucose sensor 70-180 mg/dL. The hypothesis to be tested is the R-AP closed-loop system will increase time in range and decrease AUC as compared to the MPC-AP closed-loop system. We will estimate the difference between systems using a fixed effect in a standard 2x2 crossover model with a random participant effect. While we do not anticipate statistically significant effects for the following, we will also control for sequence (AB or BA) and period (1 or 2).

We anticipate that the primary outcomes will be approximately normally distributed. We will review the appropriateness of this assumption using both goodness-of-fit tests and diagnostic plots, such as quantile-normal plots. If the normality assumption holds, possibly with a transformation of the outcome, we will test the difference between the robust-AP and standard MCP visits using a paired t-test. In the case of mild departures from normality or unequal variances at the two time points, we will re-analyze the primary outcome as the difference between the two visits using bootstrapped standard errors, which avoid distributional assumptions. We will use two-sided tests at the 0.05 level of significance.

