Missing data: Missing sensed glucose values will be interpolated for up to 30 min segments. Longer periods of missing data will be omitted if they represent <3% of observation time (which will be truncated if a participant leaves the study early). If the missing data are >3% of observation time, we will use available CBG values to interpolate or impute using measurements. In the case that >2 participants fail to complete the study, we will analyze the primary outcome under multiple imputation using baseline values.

Confidentiality and Protection of Human Subjects RISKS and BENEFITS

Risks: The risks of the protocol procedures are considered minor. Nonetheless, since pumps and sensors used within automated glucose control systems are imperfect, there is a risk for hyperglycemia and hypoglycemia All studies will have frequent glucose and ketone samplings and a member of the study staff will be present for studies with a study investigator on call at all times.

Rarely, there can be allergic responses to insulin, such as skin redness, hives, itching of the skin, swelling of the mouth, or breathing difficulties. These reactions are considered very unlikely.

There is a small risk of sensor fracture, and in such a case, a piece of the sensor could be left in the tissue after sensor removal. For this reason, the study investigator will inspect each removed sensor for the possibility of breakage or fracture. Any evidence of sensor breakage will be recorded and reported to FDA and the sensor company.

Benefits: The participant may not directly benefit from being in this study; however, their participation may help to advance automated insulin delivery technology.

COSTS:

Participants will receive \$340 for completion of all study visits. If a participant withdraws early from the study, compensation will be given as follows: \$40 for the run-in visit and \$150 for each of the 2 study visits. There is no compensation for the screening visit. If a participant is asked to repeat a study due to technical problems, he/she will receive an additional \$150.

Monitoring Entity:

This investigation will be monitored by the co- investigator [name] MD. [name] has no commercial interest in any of the companies which manufacture any of the devices used in this

IRB 23343 Protocol v5 NCT05083559

study. Drs. [name], [name] and [name] are inventors on patents regarding the algorithms.

Data Collection:

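### Do two primary endpoints, each tested at two-sided 0.05, need a stated success rule or a multiplicity adjustment?

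*Combined protocol and SAP*

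**What the plan says.** Primary Objectives lists two separate objectives: one on AUC, "as measured by area under the curve (AUC) in the 4 hours following first meal period", and one on time in range over the same window. Endpoints repeats the pair, and so does Statistical methods, which begins "The primary study endpoints are (1) incremental area under the curve (AUC) of glucose" and then adds time in range as the second.

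The hypothesis appears twice. Under Study Hypothesis, R-AP "will decrease AUC and increase the time in range as measured by sensed glucose values". Under Statistical methods: "The hypothesis to be tested is the R-AP closed-loop system will increase time in range and decrease AUC", relative to the MPC system. The error rate is given in one sentence: "We will use two-sided tests at the 0.05 level of significance".

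Two fallback analyses are described in the singular. For departures from normality, "we will re-analyze the primary outcome as the difference between the two visits using bootstrapped standard errors". For more than two non-completers, "we will analyze the primary outcome under multiple imputation using baseline values".

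Power Analysis says the study is to obtain "feasibility and assessment of variability in the primary outcomes that will inform a future larger, sufficiently powered efficacy study". The sample of 15 is justified by feasibility, without an effect size, a standard deviation or a power figure.

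**The concern.** With two primary endpoints, each tested at the full 0.05, a reader looks for the rule that combines them, and none is written as a rule. The separate objectives could be taken to mean that each endpoint supports its own claim, whereas the hypothesis wording suggests that both are needed. The singular wording in the fallback analyses adds some doubt about whether one endpoint was meant to lead.

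What is at stake is how to read a trial in which only one endpoint is significant. If success could be declared on whichever endpoint came out well, the false-positive chance in favour of R-AP would exceed the 2.5% that a single two-sided 0.05 test allows.

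**Working it through.** **Inputs.** From Statistical methods: two primary endpoints and a two-sided level of 0.05 per test, hence 0.025 in the direction favouring R-AP. From Power Analysis: n = 15. The protocol gives no correlation between the two test statistics, so r is an assumption and is shown over a range. Both statistics are signed so that positive values favour R-AP. There is no stated power or familywise figure to reproduce.

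**If both are required.** P(both) cannot exceed the smaller of the two individual probabilities. If at least one endpoint has no true effect, P(false success) ≤ 0.025, whatever r is.

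**If either suffices.** With no effect on either endpoint, P(either) = 0.025 + 0.025 − P(both).

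- Bound with no assumption on r: P(both) ≥ 0, so P(either) ≤ 0.05.
- Independence: 1 − 0.975² = 0.0494.
- Correlated, from the bivariate normal with critical value 1.96:

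| r | P(both favour R-AP) | P(either favours R-AP) |
|---|---|---|
| −0.5 | 0.0000 | 0.0500 |
| 0 | 0.0006 | 0.0494 |
| 0.5 | 0.0046 | 0.0454 |
| 0.7 | 0.0083 | 0.0417 |
| 0.9 | 0.0148 | 0.0352 |
| 0.99 | 0.0217 | 0.0283 |

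The sign of r matters: at negative r the either-endpoint figure goes to the 5.0% bound. Positive r is the more plausible case, because both endpoints come from the same CGM trace and lower post-meal glucose tends to improve both.

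**Check at the actual sample size.** Simulated paired t-tests with n = 15 (400,000 runs for each r) give P(either) of 4.9%, 4.6%, 4.0% and 3.6% at r = 0, 0.5, 0.8 and 0.9. The normal-theory values at the same r are 4.9%, 4.5%, 3.9% and 3.5%.

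**Either direction.** If a false finding against R-AP is also counted, independence gives 1 − 0.95² = 0.0975, against 0.05 for one test.

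**Which reading the text supports.** Both statements of the hypothesis join the two effects with *and*. No section says that one endpoint is enough, and none ranks them: AUC comes first in the objectives and endpoints, while time in range comes first in the Statistical methods hypothesis. The bootstrap sentence uses the singular, but its own paragraph opens by referring to the primary outcomes in the plural, so the singular reads as whichever outcome is being analysed.

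**The case for a change.** The best argument for a change is that a hypothesis is not a decision rule, and that a split result is a realistic outcome. In a simulation with n = 15 paired t-tests, an assumed r of 0.7 and assumed standardised effects of 0.3, 0.5 and 0.8 on both endpoints, exactly one endpoint was significant in favour of R-AP in about 18%, 26% and 17% of trials. One added sentence would settle the reading at almost no cost.

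It is true that the rule is not written out and that a split result could well occur. But the sentence that matches the hypothesis would only restate what its *and* already implies. Making AUC a gatekeeper for time in range would be a new choice: the protocol does not rank the endpoints, and reasonable statisticians would differ on it in a feasibility study. Nor is the error rate left open. Even if the reading were chosen after seeing the data, the worst case is the either-endpoint rule, capped at 5.0% in favour of R-AP. A split result would ordinarily be reported as two differences with confidence intervals, which is what a study meant to estimate outcomes and their variability needs.

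**Conclusion.** No change follows. Under the conjunctive hypothesis that the protocol states twice, testing each endpoint at two-sided 0.05 is sound without adjustment, and a false success favouring R-AP has at most a 2.5% chance. Under the either-endpoint reading, which no section states, the chance would be at most 5.0%, and about 4.9% to 3.5% if r lies between 0 and 0.9; that range of r is assumed. The missing decision rule is a detail that analysts can fill from the hypothesis, and the singular wording in the fallback analyses is clerical. The conclusion rests on reading *and* as requiring both effects, and on the stated feasibility purpose. It would be different for a confirmatory trial meaning to claim success on either endpoint.

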Participants will be recruited from OHSU clinics, from flyers to be posted in approved places at OHSU or posted on the web to the clinical trials page for the OHSU Schnitzer Diabetes Clinic, to the Clinic's facebook group, ads on Facebook, electronic newletter or from the OHSU Subject Recruitment website. Handouts may also be made available to faculty at Tuality, Providence, Kaiser and Legacy to pass along to patients/participants who show interest in the study. Records from OHSU Schnitzer Diabetes Clinic patients may be screened to find potential participants. Participants will also be recruited from a list of participants who participated in past OHSU studies who have agreed to be contacted regarding future studies, from the OHSU diabetes research registry and/or www.clinicaltrials.gov. Participants will be contacted using the approved telephone screening script and email template. Non-english speaking participants will not be recruited since this protocol would require the use of medical devices and mobile software that do not have non-english versions available.

Up to 18 participants may be screened in this study. Goal enrollment is 15 participants.

Withdrawal Criteria

The participant may withdraw at will at any time or at the discretion of the Investigator. A participant must be withdrawn if the following applies:

- Hypoglycemia during the treatment period posing a safety problem as judged by the investigator.
- Hyperglycemia during the treatment period posing a safety problem as judged by the investigator.
- Protocol deviation having influence on efficacy or safety data as judged by the Investigator.
- Substantial and repeated non-compliance with trial procedures.
- Pregnancy.
- Intention of becoming pregnant.

Visit Procedures

Negative COVID-19 screening is required for face-to-face visits. Study staff will perform COVID-19 screening on all participants and participant households, to ensure that there is no COVID-19 or COVID-19 symptoms. OHSU COVID-19 policy provides the option to complete visits virtually in order to minimize face-to-face contact with participants.

Screening (Visit 1)

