After a run-in period of 2 hours whereby the participants are using the AP algorithms, participants will eat self selected meals around 10 am. During the R-AP study only, another meal will be given four hours later around 2 pm. The self selected meals will have a minimum of 45 g of carbohydrates, and a maximum of 120 g of carbohydrates. These self selected breakfasts will be identical across both study sessions. Participants will not enter a meal bolus for the meals. CBG and blood ketone measurements will be taken every 30 min (for safety purposes only, not for input into the AP systems) until study discharge. If CBG >250mg/dL before the lunch meal, then study will be stopped early and the participant will be given the option to return on a different day for the second meal.

The study will be stopped if:

- (1) the CBG reaches > 300 mg/dL with ketones > 0.5 mM,
- (2) the CBG reaches > 300 mg/dL for over an hour (even when ketones are <0.5 mM),
- (3) the CBG reaches > 450 mg/dL,
- (4) participants exhibit nausea or vomiting or both.

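### Truncating observation time does not fit a 4-hour iAUC that is a sum, and the plan does not say that CGM after a high-glucose stop is used to 240 minutes

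*Combined protocol and SAP*

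**What the plan says.** - **Endpoints.** The first primary endpoint is the iAUC (mg/dL*min) over four hours from the start of the first meal. The calculation "sums all CGM values in the 4 hour period following the meal above the starting glucose"; nothing divides it by time. The second is the percent of those four hours with sensed glucose at 70-180 mg/dL. The secondary list, also tied to the 4-hour post-meal period, includes "Number of provider-administered insulin injections due to hyperglycemia".
- **1 day Treatment Visits, stops.** Meals contain 45-120 g of carbohydrate and no meal bolus is entered. Among other reasons, a visit stops if "the CBG reaches > 300 mg/dL with ketones > 0.5 mM" (rule 1), if "the CBG reaches > 300 mg/dL for over an hour (even when ketones are <0.5 mM" (rule 2), or if CBG exceeds 450 mg/dL (rule 3).
- **1 day Treatment Visits, after a stop.** Under rules (1)-(3) the investigator works out a meal-plus-correction bolus, and CGM continues to be watched. "CBG and blood ketone measurements will be taken every 30 min", and this is "for safety purposes only, not for input into the AP systems) until study discharge". Discharge is possible after 4 pm, and the sensor comes off at discharge.
- **Withdrawal Criteria.** Withdrawal is mandatory for "Hyperglycemia during the treatment period posing a safety problem as judged by the investigator".
- **Statistical methods, Missing data.** Gaps up to 30 minutes are interpolated. Longer gaps are dropped if they are under 3% of "observation time (which will be truncated if a participant leaves the study early"; above 3%, CBG is used. Multiple imputation from baseline values applies only if more than two participants do not complete.
- **Repeat visits.** Discharge from clinic offers an optional repeat after a premature stop, with technical problems as its example. COSTS sets a repeat payment for technical problems only. Neither says which attempt is analysed.

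**The concern.** A percentage can survive a shorter denominator, with some distortion. A sum cannot: it falls with every minute removed. The early-exit wording in the missing-data rule shortens the record and makes no allowance for this. The visits at risk are those with the highest glucose, so the error follows the outcome: a visit ended because control failed can score better than a milder visit that ran to the end.

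The safeguard in the plan does not catch this. Once observation time is cut, the missing minutes are no longer in the 3% denominator, so the CBG fill is not triggered. For an on-site stop those CBG readings exist.

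It is also unclear whom the wording covers. A participant withdrawn for hyperglycemia fits it directly. A participant whose visit is stopped but who stays in the clinic may not. Nor does the plan say whether a stopped visit counts as non-completion for the imputation trigger. Two analysts could score the same visit very differently on both primary endpoints.

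The study makes no powered claim. Its purpose is to estimate the outcomes and their variability for a larger trial, so what is at stake is the effect estimate and SD passed on.

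**Working it through.** The plan gives no SD, effect size or stop rate, so there is no stated figure to reproduce. The curves below are assumptions that show mechanism and scale only.

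**1. Is there CGM to use after an on-site stop?** The first meal is at about 10 am, so the window ends at about 2 pm. Discharge is after 4 pm and the sensor is worn until then. Yes.

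**2. What does the 3% rule do?** With a 240-minute denominator, 3% is 0.03 x 240 = 7.2 min. A gap over 30 min exceeds 30/240 = 12.5%, so it would always go to CBG. With a truncated denominator the minutes after the cut count as zero missing.

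**3. Assumed curve.** Start 140 mg/dL, linear rise to 310 at 90 min, then flat. For a record ending at s >= 90 min:

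iAUC(s) = 170 x 90/2 + 170 x (s - 90) = 7,650 + 170(s - 90).

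Time at or below 180 is 40/170 x 90 = 21.2 min. The first 30-minute CBG above 300 is at 90 min. A rule (1) stop is therefore at 90 min if ketones qualify. A rule (2) stop is at 150 or 180 min, depending on how the one-hour condition is read.

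| Record | iAUC | vs full | Time in range |
|---|---|---|---|
| Full 240 min, no rescue | 33,150 | - | 21.2/240 = 8.8% |
| Cut at 180 | 22,950 | -31% | 21.2/180 = 11.8% |
| Cut at 150 | 17,850 | -46% | 21.2/150 = 14.1% |
| Cut at 90 | 7,650 | -77% | 21.2/90 = 23.5% |

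A milder completed visit (same start and rise time, plateau 280) scores 140 x 90/2 + 140 x 150 = 27,300. All three cut records fall below it.

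**4. Would rescaling to 240 min repair the sum?** No. 17,850 x 240/150 = 28,560 (-14%) and 7,650 x 240/90 = 20,400 (-38%), because the early rise is over-represented.

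**5. One truncated visit in a 15-person arm mean.** For iAUC: (33,150 - 22,950)/15 = 680; (33,150 - 17,850)/15 = 1,020; (33,150 - 7,650)/15 = 1,700 mg/dL*min. For time in range: about 0.2, 0.35 and 1.0 points.

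**6. CGM kept to 240 min.** Assume glucose holds until 30 or 60 min after the stop, then falls 1, 2 or 3 mg/dL/min to a floor of 100.

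| Stop | iAUC | Below unrescued | Time in range |
|---|---|---|---|
| 150 or 180 min | 27,767 to 33,150 | 0-16% | 8.8 to 15.8% |
| 90 min | 17,567 to 29,100 | 12-47% | 8.8 to 40.8% |

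For the later stops the ranking against 27,300 is kept. For the 90-minute stop it is lost in 5 of 6 settings. The extreme time-in-range value comes from a fall of 3 mg/dL/min starting at 120 min: glucose re-enters range after 130/3 = 43.3 min, so (76.7 + 21.2)/240 = 40.8%.

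**7. Other assumed curves under truncation.** With starts 100-180, plateaus 310-400 reached at 60-120 min, rule (2) cuts lose 17-62% of iAUC and rank below the milder completed visit in 37 of 54 cases. Rule (1) cuts lose 67-90% and do so in 27 of 27. Time in range rises by 0-10 and 0-29 points. These are counts of chosen curves, not probabilities. Rules (3) and (4) were not computed.

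**The case against.** **The early-exit wording only qualifies the 3% test, and on-site stops are not departures.** Much of this stands. The endpoint definition fixes the 4-hour window, the secondary list counts provider injections within it, CGM is watched after a stop, and discharge comes later. Using CGM to 240 minutes is the more natural reading for a stopped participant on site. A reader might infer that the plan truncates every high-glucose stop; the documents do not say that. The large losses need truncation, which fits directly only someone who is withdrawn or leaves. What remains is that the one rule on early exit does not say which case applies, and it gives a wrong iAUC wherever it is used.

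**CGM after investigator insulin is not biased.** This stands if the target is glucose regardless of rescue. A reader might infer that either way of scoring understates the iAUC; for kept CGM that is so only against what the system alone would have produced. The plan names neither target.

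**Keeping post-stop CGM has a cost on time in range.** This stands. For a stop at 90 min, three of the six settings (28.3, 31.8 and 40.8%) lie further from the unrescued 8.8% than the truncated 23.5% does.

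**The curves never fall, although closed-loop insulin is running.** This stands as a limit on size. If the same curve falls 0.3 mg/dL/min after its peak, it is above 300 for about 39 min (5.3 min rising, 33.3 min falling) and rule (2) does not fire.

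**Repeats are meant for technical failures.** COSTS supports this, but the open-ended example under Discharge from clinic leaves room for doubt.

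**Conclusion.** The concern holds in a limited form. Truncation is the wrong operation for an iAUC that is an undivided 4-hour sum. Applied to a participant withdrawn for hyperglycemia or to a visit stopped under rules (1)-(3), it gives too low an iAUC, usually too high a time in range, and bypasses the CBG fill. For a stopped participant still on site, the documents lean towards full-window CGM but do not state it, nor which quantity that CGM estimates.

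In the main illustration truncation costs 31-77% of the iAUC. Kept CGM is 0-16% below the unrescued value for stops at 150-180 min and 12-47% below for a stop at 90 min. All of this rests on assumed curves that plateau without falling. It might be inferred that the error favours R-AP, or that it penalises it. The documents support neither, because the direction depends on which arm stops more and no stop rates are given. For a 15-person feasibility study this should be fixed before analysis; it does not threaten the design.

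**What to change.** Replace the parenthesis on truncation under Missing data with:

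> For both primary endpoints the window and the denominator are the 240 minutes from the start of the first meal. A stopped visit is not truncated: CGM recorded after the stop is used, and gaps over 30 minutes are filled from CBG. A partial iAUC is not compared with full-window values. If neither CGM nor CBG reaches 240 minutes, the endpoint is missing and is handled by the planned multiple imputation, whatever the number of such participants.

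Also:

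- State that the main estimate is glucose regardless of investigator insulin.
- Report stops, reasons, times and provider insulin by arm.
- Add one sensitivity analysis for visits stopped for high glucose or ketones, for example worst rank in the same crossover model. Label it a robustness check that does not supply the effect size or SD for the larger study.
- State that a repeat replaces a stopped visit only after technical failure. Otherwise analyse the first attempt and report the repeat separately, because replacing it would select on the outcome.

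The cost is SAP wording and one extra analysis. The CGM and CBG are already planned, and no clinical stopping rule changes. In the illustration, filling all post-stop CGM from 30-minute CBG shifts the iAUC by 0 to -1.5%, with an SD of 2-3% under an assumed 5% meter error.

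The downside should be stated. For a stop at 90 min in the illustration, kept CGM gives an iAUC up to 47% below and a time in range up to 32 points above (40.8 - 8.8) the unrescued values. For stops at 150-180 min the differences are 0-16% and 0-7 points (15.8 - 8.8). This is why the sensitivity result belongs beside the main one.
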